7.4.2 Changes in MRI

The CRF collects investigator reported presence or absence of changes in head MRI images at follow-up visits. When changes are reported in MRI images post baseline, details of the event are reported as an AE. The MRI listing includes an indication of presence or absence of changes in MRI images at follow-up visits.

This Document is Company Confidential Page 16 of 28

7.4.3 Laboratory Data

All safety laboratory evaluations will be conducted at the laboratories located at or associated with the clinical site. Laboratory values will include hematology, serum chemistry, INR, plasma cytokines, and lipid panels. Descriptive statistics (N, mean, SD, median, minimum, and maximum) will be presented for qualitative laboratory values. Laboratory values will be assessed for change from baseline by visit. All treatmentemergent abnormal chemistry and hematology values meeting toxicity criteria will be summarized by test across study visits. Toxicity criteria are defined in Appendix 10.2.

The absolute and change from baseline results for each laboratory test will be summarized. Patients with missing data for a given time point will not contribute to the tabulations for that time point. Data listings will include all laboratory results by patient by visit. Patients with values above or below the reference range will be identified in the data listings with flags for high and low values.

A listing of the normal reference ranges will be included.

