5.2 Monitoring for Humoral or Cell-Mediated Immune Response

In the Ph. 1/2a clinical study, Patients will be evaluated on Day 8 after implantation, monthly thereafter through month 4, and then at months 6, 9, 12 and 24 for any symptoms of inflammation, humoral immune response, or cell-mediated immune response (see Table 4). The parameters to be followed are: vital signs, hematology, serum chemistry, lipid panel, cytokine levels (TNF- α , IL-6, IFN- γ), CRP, head MRI, antibodies to SB623, and PBMC function (see Section 15.0).

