15.3 Safety Laboratory

All safety laboratory evaluations will be conducted at the laboratories located at or associated with the clinical site. At every sampling time point, approximately 5 mL of blood will be drawn for each of the hematology and serum chemistry panels.

The following laboratory evaluations will be performed:

- Hematology Panel: hematocrit, hemoglobin, WBC, platelet count, lymphocyte count, neutrophil count
- Serum Chemistry Panel: sodium, chloride, calcium, potassium, magnesium, bicarbonate, lactate, C-reactive protein, glucose, creatinine, BUN, AST, ALT, alkaline phosphatase, and total bilirubin
- Lipid Panel: total cholesterol, LDL cholesterol, HDL cholesterol, and triglycerides
- Cytokines: Plasma TNF-α, Plasma IL-6, and Plasma IFN-γ
- INR

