Table 14.2.8.20	Cognitive Function Test Battery, Beck Anxiety Inventory	ITT
Table 14.3.1.1	Treatment-Emergent Adverse Events by MedDRA Primary System Organ Class and Preferred Term, by Decreasing Frequency	Safety
Table 14.3.1.2	Treatment-Emergent Adverse Events by Maximum Severity, by MedDRA Primary System Organ Class and Preferred Term, by Decreasing Frequency	Safety
Table 14.3.1.3	Treatment-Emergent Adverse Events by Relationship to Study Treatment, by MedDRA Primary System Organ Class and Preferred Term, by Decreasing Frequency	Safety
Table 14.3.1.4	Adverse Events Resulting in Discontinuation from the Study by MedDRA Primary System Organ Class and Preferred Term, by Decreasing Frequency	Safety
Table 14.3.1.5	Serious Adverse Events by MedDRA Primary System Organ Class and Preferred Term, by Decreasing Frequency	Safety
Table 14.3.4.1	Chemistry Laboratory Results, Change from Baseline by Visit	Safety
Table 14.3.4.2	Treatment-Emergent Abnormal Chemistry Laboratory Results across Visits	Safety
Table 14.3.4.3	Hematology Laboratory Results, Change from Baseline by Visit	Safety
Table 14.3.4.4	Treatment-Emergent Abnormal Hematology Laboratory Results across Visits	Safety
Table 14.3.4.5	Lipid Panel Laboratory Results, Change from Baseline by Visit	Safety
Table 14.3.4.6	Treatment-Emergent Abnormal Lipid Panel Laboratory Results across Visits	Safety
Table 14.3.4.7	Serum PBMC Cytokine Results, Change from Baseline by Visit	Safety
Table 14.3.4.8	Plasma Cytokine Results, Change from Baseline by Visit	Safety
Table 14.3.4.9	INR Laboratory Results, Change from Baseline by Visit	Safety
Table 14.3.5.1	Pulse Rate, Change from Baseline by Visit	Safety
Table 14.3.5.2	Diastolic Blood Pressure, Change from Baseline by Visit	Safety
Table 14.3.5.3	Systolic Blood Pressure, Change from Baseline by Visit	Safety
Table 14.3.5.4	Oral Temperature, Change from Baseline by Visit	Safety
Table 14.3.5.5	Respiration Rate, Change from Baseline by Visit	Safety

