10.2 CLINICALLY NOTABLE ABNORMAL VALUES

WHO (World Health Organization) Toxicity Criteria by Grade

Category	Toxicity	Grade 0	Grade 1	Grade 2	Grade 3	Grade 4
Haematology	WBC (x103/l)	4	3.0 - 3.9	2.0 - 2.9	1.0 - 1.9	< 1.0
Haematology	Platelets (x103/l)	WNL	75.0 - normal	50.0 - 74.9	25.0 - 49.9	< 25.0
Haematology	Haemoglobin (g/dl)	WNL	10.0 - normal	8.0 - 9.9	6.5 - 7.9	< 6.5
Haematology	Granulocytes/ Bands (x103/l)	2	1.5 - 1.9	1.0 - 1.4	0.5 - 0.9	< 0.5
Haematology	Lymphocytes (x103/l)	2	1.5 - 1.9	1.0 - 1.4	0.5 - 0.9	< 0.5
Haematology	Haemorrhage	none	mild, no	gross, 1 - 2 units transfusion per episode	gross, 3 - 4 units transfusion per episode	massive, > 4 units transfusion per episode
Coagulation	Fibrinogen	WNL	0.99 - 0.75 x N	0.74 - 0.50 x N	0.49 - 0.25 x N	< 0.25 x N
Coagulation	Prothrombin time(Quick)	WNL	1.01 - 1.25 x N	1.26 - 1.50 x N	1.51 - 2.00 x N	> 2.00 x N
Coagulation	Partial thromboplastin time	WNL	1.01 - 1.66 x N	1.67 - 2.33 x N	2.34 - 3.00 x N	> 3.00 x N
Metabolic	Hyperglycaemia (mg/dl)	< 116	116 - 160	161 - 250	251 - 500	> 500 or ketoacidosis
Metabolic	Hypoglycaemia (mg/dl)	> 64	55 - 64	40 - 54	30 - 39	< 30
Metabolic	Amylase	WNL	< 1.5 x N	1.5 - 2.0 x N	2.1 - 5.0 N	> 5.0 x N
Metabolic	Hypercalcaemia	< 10.6	10.6 - 11.5	11.6 - 12.5	12.6 - 13.4	13.5

Category	Toxicity	Grade 0	Grade 1	Grade 2	Grade 3	Grade 4
	(mg/dl)					
Metabolic	Hypocalcaemia (mg/dl)	> 8.4	8.4 - 7.8	7.7 - 7.0	6.9 - 6.1	6
Metabolic	Hypomagnesaemia (mg/dl)	> 1.4	1.4 - 1.2	1.1 - 0.9	0.8 - 0.6	0.5
Liver	Bilirubin (N = 17 μmol/L)	WNL		< 1.5 x N	1.5 - 3.0 x N	> 3.0 x N
Liver	Transaminase (SGOT, SGPT)	WNL	2.5 x N	2.6 - 5.0 x N	5.1 - 20.0 x N	> 20.0 x N
Liver	Alk Phos or 5 nucleotidase	WNL	< 2.5 x N	2.6 - 5.0 x N	5.1 - 20.0 x N	> 20.0 x N
Liver	Liver- clinical	No change from baseline			precoma	hepatic coma
Kidney, bladder	Creatinine	WNL	< 1.5 x N	1.5 - 3.0 x N	3.1 - 6.0 x N	> 6.0 x N
Kidney, bladder	Proteinuria	No change	1 (+) or < 0.3 g% or 3 g/L	2 - 3 (+) or 0.3 - 1.0 g% or 3 - 10 g/L	4 (+) or > 1.0 g% or > 10g/L	nephrotic syndrome

Statistical Analysis Plan Addendum

SanBio Incorporated Protocol SB-STR01

SANBIO INCORPORATED [name] [contact]

Protocol SB-STR01

A Phase 1/2A Study of the Safety and Efficacy of Modified Stromal Cells (SB623) in Patients with Stable Ischemic Stroke

Statistical Analysis Plan Addendum

Final 1.0

Date: 14DEC2016

Prepared by: [name]

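### The treatment-emergent laboratory tables cannot count 8 of 21 chemistry and hematology analytes or any high blood count, and the lipid table has no stated criterion

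*SAP*

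**What the plan says.** SAP section 7.4.3 states: "All treatmentemergent abnormal chemistry and hematology values meeting toxicity criteria will be summarized by test across study visits". It then adds: "Toxicity criteria are defined in Appendix 10.2". That appendix, headed "CLINICALLY NOTABLE ABNORMAL VALUES", reproduces part of the WHO toxicity table from protocol Appendix C.

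Protocol section 15.3 defines the panels that are drawn. The largest, with 15 tests, is given as "Serum Chemistry Panel: sodium, chloride, calcium, potassium, magnesium, bicarbonate, lactate, C-reactive protein, glucose, creatinine, BUN, AST, ALT, alkaline phosphatase, and total bilirubin". The same section also sets out a hematology panel of six tests and a lipid panel of four.

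The schedule (protocol Table 4, SAP Appendix 10.1) repeats these three panels at every follow-up visit from Day 8 to Month 24. INR is scheduled only at Screening 1 and Baseline.

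SAP section 9.2 plans three tables of treatment-emergent laboratory abnormalities: 14.3.4.2 (chemistry), 14.3.4.4 (hematology) and 14.3.4.6, titled "Treatment-Emergent Abnormal Lipid Panel Laboratory Results across Visits". It also plans Table 14.3.4.9, INR change from baseline by visit.

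Protocol section 5.2 has patients evaluated after implantation "for any symptoms of inflammation, humoral immune response, or cell-mediated immune response", and names hematology, serum chemistry, the lipid panel and CRP among the parameters to follow.

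**The concern.** A rule that counts an abnormality only when it meets a grade is complete only if the grading table covers every analyte, in each direction of interest. Appendix 10.2 does not.

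The gaps fall on results that matter here. The cells are allogeneic and are given without immunosuppression, and the protocol relies on CRP and hematology, among other measures, to detect inflammation. A rise in CRP, white cells or neutrophils is exactly what the counting tables cannot record. Nor can they record any change in sodium or potassium after intracranial surgery. A reader who finds no such entries in Tables 14.3.4.2 and 14.3.4.4 could take a missing criterion for a missing event.

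**Working it through.** The documents give no figure for this coverage, so there is none to reproduce. The check matches each analyte in protocol 15.3 to the rows of SAP Appendix 10.2. Neutrophils are matched to the granulocytes/bands row, and AST and ALT to the transaminase row.

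| Panel | Analytes | With a row | Without a row |
|---|---|---|---|
| Hematology | 6 | 5: hemoglobin, WBC, platelets, lymphocytes, neutrophils | 1: hematocrit |
| Chemistry | 15 | 8: calcium, magnesium, glucose, creatinine, AST, ALT, alkaline phosphatase, bilirubin | 7: sodium, chloride, potassium, bicarbonate, lactate, CRP, BUN |
| Lipids | 4 | 0 | 4: total, LDL and HDL cholesterol, triglycerides |

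**Coverage.** Within the scope of the 7.4.3 sentence (chemistry and hematology), the analytes without a row are 1 + 7 = 8 of 6 + 15 = 21, or 38%. Adding the lipids gives 8 + 4 = 12 of 25, or 48%. Adding the three plasma cytokines would give 15 of 28, or 54%, but no abnormality table is planned for them, so they are left out.

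**Direction.** All five graded hematology rows worsen as the value falls, so 0 of 5 have a high-side criterion. Magnesium has a row for low values only. Calcium and glucose are graded in both directions.

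**What each table can show.**

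- Table 14.3.4.2: 8 of 15 chemistry analytes, and magnesium only when low.
- Table 14.3.4.4: 5 of 6 hematology analytes, all only when low.
- Table 14.3.4.6: undefined. The 7.4.3 sentence does not name lipids, and Appendix 10.2 has no lipid row.

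**Text extraction.** The SAP appendix ends after proteinuria in the available text. The fuller protocol Table 6 has no row for any of the 12 analytes either, so the count does not depend on where the SAP copy stops.

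**INR.** SAP section 5 defines baseline as the last assessment before treatment. With INR scheduled only at Screening 1 and Baseline, Table 14.3.4.9 has no scheduled post-implant value from which to compute a change. This comes from the visit schedule and has nothing to do with Appendix 10.2.

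**The case against.** The best defense is that these values are not lost.

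- **Listings.** SAP 7.4.3 lists every result by patient and visit, with high and low flags. SAP 7.4 also marks clinically significant out-of-range values.
- **Descriptive summaries.** Absolute values and changes are summarized for each test, with minimum and maximum. One extreme CRP in a cohort of 6 would show as the maximum.
- **Adverse events.** Protocol 16.1 makes a laboratory abnormality an adverse event if it worsened from baseline and the investigator judges it clinically significant. It would then enter the treatment-emergent adverse event tables. Protocol Appendix C has a generic severity scale for events without a WHO row.
- **Decisions.** Dose-limiting toxicity and cohort stopping rest on graded related events and DSMB review, not on these tables.

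All of this stands, and it rules out two stronger readings. A reader might infer that several safety tables are empty by construction. They are not: chemistry and hematology are partly covered, and only the lipid table lacks any criterion. A reader might also infer that the report would show no such abnormalities whatever happened. It would not, given the three routes above.

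The defense does not restore the count. Listings are read patient by patient and give no incidence. Laboratories are local, at up to 8 sites, so a pooled maximum cannot be set against one reference range and does not say how many patients were abnormal. The adverse event route depends on investigator judgment, and its window is inconsistent: 24 weeks in protocol 16.2, 24 months in SAP 7.4.1. The generic scale grades activity limitation, need for intervention and hospitalization. It can grade a reported event but cannot be programmed from a laboratory number, and SAP Appendix 10.2 omits it. SAP 7.4 promises the incidence of clinically significant laboratory changes, yet section 9.2 has no laboratory table that tabulates those marks.

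**Conclusion.** The point holds as a gap in coverage. Followed exactly, the 7.4.3 rule leaves 8 of 21 chemistry and hematology analytes (38%), every high blood count and high magnesium out of the only planned laboratory tables that count abnormal values. The lipid table has no stated criterion. The 48% figure (12 of 25) is correct for the three panels together, but should not be attributed to the 7.4.3 sentence, which does not cover lipids. The INR table is a separate, smaller defect of scheduling.

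This rests on reading Appendix 10.2 as the sole source of the criteria, as 7.4.3 says, and on the row matching shown above. It is worth correcting because safety is the primary objective and the omitted signals include those that protocol 5.2 monitors. It does not affect the dose-limiting toxicity definition or the stopping rules.

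**What to change.** In SAP 7.4.3, add a rule for any analyte or direction without an Appendix 10.2 grade, including all lipids. Under it, a treatment-emergent abnormality is a post-implant value outside the site reference range that was within the range, or less far outside it, at baseline. Keep the Appendix 10.2 grades where they exist, and label which definition each row uses.

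Tabulate low and high values separately in Tables 14.3.4.2, 14.3.4.4 and 14.3.4.6. Delete Table 14.3.4.9 or retitle it as a screening and baseline summary.

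The cost is SAP wording and programming. The reference ranges and high/low flags are already planned for the listings, so no new data are needed. The downside is that more minor out-of-range values will appear in the tables. If the tables have already been produced, the added counts can be issued as supplementary output.

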7.4.4 Vital Signs

Vital signs will include oral temperature, blood pressure at rest, heart rate, and respiratory rate. Weight is summarized under physical exam. Vital signs will be assessed for change from baseline by visit. Patients with missing data for a given time point will not contribute to the tabulations for that time point. Changes from baseline values will be presented.

A listing of all vital signs will be included.

7.4.5 Physical Exam

Physical exam of the following body categories occurs at screen 1; general appearance, skin, HEENT, neck (including thyroid), heart, lungs, abdomen, lymph nodes, extremities, neurological assessment, musculoskeletal system, and other as specified on CRF. Subsequent visits require physical exam assessment only if significant change since screen 1 occurs for one of the specified body categories. Weight is recorded at Screening 1, Follow-up Month 12, and End of Study.

A listing of physical exam assessments including weight will be included.

7.4.6 Antibody Activity

A blood sample, taken at initial screening to determine patient eligibility, will be used to determine the presence of antibodies to donor SB623 cells: HLA Class I (HLA-A 36XX, HLA-A 68XX, HLA-B53XX, or HLA-B*5802) or Class II (DRB1*1101 (DR11) or DRB1*12CVT (DR12)). Serum antibody measurements are then taken throughout the study at time points indicated in Appendix 9.1.

Presence of antibodies to SB623 will be indicated in the antibody listing by patient by visit.

7.4.7 PBMC and Cytokines

PBMC function during the study will be evaluating any changes from baseline in cytokine secretion (Serum TNF- α , Plasma IL-6, and Plasma IFN- γ).

This Document is Company Confidential Page 17 of 28 PBMC function, the cytokine secretion results, will be listed by patient by visit.

7.5 INTERIM ANALYSIS

One interim analysis is planned, which will be performed when the last patient enrolled in the study, has completed their Month 6 visit. This interim analysis will be based on the Month 6 data and will include all tables, listings, and figures.

7.6 DATA SAFETY AND MONITORING BOARD

The members of the Data Safety and Monitoring Board (DSMB) will be experts who are independent from the sponsor, formed to continuously evaluate toxicity and mortality rates. The procedures and responsibilities for the collection, analysis, and review of the data by the DSMB as well as communication and documentation of their opinions and recommendations are defined in the DSMB charter.

The DSMB will review the safety profile of all patients in each cohort. If the safety profile is deemed acceptable by the DSMB for a given cohort, the first patient in each subsequent cohort will be dosed, beginning 4 weeks after dosing of the last patient of the prior cohort. Two or more serious adverse events will trigger a review by the DSMB before continuing enrollment. Each DLT will be evaluated by the DSMB. The DSMB shall be the final arbitrator for attributions.

9. TABLES, LISTINGS, AND FIGURES FOR EACH COHORT AND COMBINED COHORTS

9.1 **PROGRAMMING SPECIFICATIONS**

Unless otherwise noted, the following conventions should be used when programming the analysis tables, listings, and figures:

- Listings should be sorted by dose group and the unique patient identifier
- Repeat footnotes on all pages of tables and listings
- Leading 0 will be shown for all values between -1 and 1.
- For the presentation of frequency and percentage data, events with the frequency of zero should be presented as the count only (i.e., presented as "0" instead of "0 (0%)").
- Percentages should be calculated based on patients with non-missing data, unless specified otherwise.
- When adverse events are reported, the MedDRA version will be reported in the footnote, similarly when medications are reported, the WHODD version will be reported in the footnote.
- The date format for all presentations will be 'DDMMMYYYY'.
- The header on all tables, listings and figures will include: Sponsor name and Protocol number(Left); Page X of Y (Right), TLF Number and Title
- The footer on all tables, listings and figures will include: SAS program path and file name, Date/Time output generated

Number	Title	Population		
Table 14.1.1	Patient Enrollment	All Patients		
Table 14.1.2	Patient Disposition	All Patients		
Table 14.1.3	Patient Disposition by Visit	All Patients		
Table 14.1.4	Patient Demographics	All Patients		
Table 14.1.5	Medical History, by MedDRA Primary System Organ	All Patients		
	Class and Preferred Term, by Decreasing Frequency			
Table 14.1.6	Concomitant Medication	All Patients		
Table 14.2.1.1	ESS Total Score, 6 Month Evaluation	ITT		
Table 14.2.1.2	ESS Motor Function Total Score, 6 Month Evaluation	ITT		
Table 14.2.2	FDG-PET Results – FDG Uptake, 6 Month Evaluation	ITT		
Table 14.2.3.1	ESS Total Score, Change from Baseline by Visit	ITT		
Table 14.2.3.2	ESS Motor Function Total Score, Change from Baseline	ITT		
	by Visit			
Table 14.2.4.1	FDG-PET Results – FDG Uptake, Change from	ITT		

9.2 LIST OF TABLES

	Baseline by Visit	
Table 14.2.4.2	FDG-PET Results – Tissue Ratio, Change from	ITT
	Baseline by Visit	
Table 14.2.5.1	NIHSS Total Score, Change from Baseline by Visit	ITT
Table 14.2.5.2	NIHSS Motor Function Total Score, Change from	ITT
	Baseline by Visit	
Table 14.2.5.3	NIHSS Motor Function Upper Extremity Affected Side,	ITT
	Change from Baseline by Visit	
Table 14.2.5.4	NIHSS Motor Function Lower Extremity Affected Side,	ITT
	Change from Baseline by Visit	
Table 14.2.6	MRS Assessment, Change from Baseline by Visit	ITT
Table 14.2.7.1	Fugl-Meyer Total Score, Change from Baseline by Visit	ITT
Table 14.2.7.2	Fugl-Meyer Motor Function Total Score, Change from	ITT
	Baseline by Visit	
Table 14.2.7.3	Fugl-Meyer Upper Extremity Motor Function Total	ITT
	Score, Change from Baseline by Visit	
Table 14.2.7.4	Fugl-Meyer Lower Extremity Motor Function Total	ITT
	Score, Change from Baseline by Visit	
Table 14.2.8.1	Cognitive Function Test Battery, Wechsler Abbreviated	ITT
	Scale of Intelligence (WASI) 2 Test	
Table 14.2.8.2	Cognitive Function Test Battery, Controlled Oral Word	ITT
	Association Category	
Table 14.2.8.3	Cognitive Function Test Battery, Vocabulary (WASI)	ITT
Table 14.2.8.4	Cognitive Function Test Battery, Trails A Time	ITT
Table 14.2.8.5	Cognitive Function Test Battery, Digit Vigilance	ITT
	Accuracy	
Table 14.2.8.6	Cognitive Function Test Battery, Rey Auditory	ITT
	Learning Test	
Table 14.2.8.7	Cognitive Function Test Battery, Rey Complex Figure	ITT
Table 14.2.8.8	Cognitive Function Test Battery, Logical Memory –	ITT
	WMS-III	
Table 14.2.8.9	Cognitive Function Test Battery, Trails B Time and	ITT
	Errors	
Table 14.2.8.10	Cognitive Function Test Battery, Letter-Number	ITT
	Sequencing WMS-III	
Table 14.2.8.11	Cognitive Function Test Battery, Rey Complex Figure	ITT
	Сору	
Table 14.2.8.12	Cognitive Function Test Battery, Matrix Reasoning	ITT
	WASI	
Table 14.2.8.13	Cognitive Function Test Battery, Digit Vigilance Time	ITT
Table 14.2.8.14	Cognitive Function Test Battery, Trails A Errors	ITT
Table 14.2.8.15	Cognitive Function Test Battery, Digit Symbol	ITT
	Substitution Test – WAIS 3	
Table 14.2.8.16	Cognitive Function Test Battery, Grooved Pegboard	ITT
Table 14.2.8.17	Cognitive Function Test Battery, Stroop Interference	ITT

Table 14.2.8.18	Cognitive Function Test Battery, Controlled Oral Word Association (FAS)	ITT
Table 14.2.8.19	Cognitive Function Test Battery, Beck Depression	ITT
Table 14.2.8.20	Cognitive Function Test Battery, Beck Anxiety Inventory	ITT
Table 14.3.1.1	Treatment-Emergent Adverse Events by MedDRA Primary System Organ Class and Preferred Term, by Decreasing Frequency	Safety
Table 14.3.1.2	Treatment-Emergent Adverse Events by Maximum Severity, by MedDRA Primary System Organ Class and Preferred Term, by Decreasing Frequency	Safety
Table 14.3.1.3	Treatment-Emergent Adverse Events by Relationship to Study Treatment, by MedDRA Primary System Organ Class and Preferred Term, by Decreasing Frequency	Safety
Table 14.3.1.4	Adverse Events Resulting in Discontinuation from the Study by MedDRA Primary System Organ Class and Preferred Term, by Decreasing Frequency	Safety
Table 14.3.1.5	Serious Adverse Events by MedDRA Primary System Organ Class and Preferred Term, by Decreasing Frequency	Safety
Table 14.3.4.1	Chemistry Laboratory Results, Change from Baseline by Visit	Safety
Table 14.3.4.2	Treatment-Emergent Abnormal Chemistry Laboratory Results across Visits	Safety
Table 14.3.4.3	Hematology Laboratory Results, Change from Baseline by Visit	Safety
Table 14.3.4.4	Treatment-Emergent Abnormal Hematology Laboratory Results across Visits	Safety
Table 14.3.4.5	Lipid Panel Laboratory Results, Change from Baseline by Visit	Safety
Table 14.3.4.6	Treatment-Emergent Abnormal Lipid Panel Laboratory Results across Visits	Safety
Table 14.3.4.7	Serum PBMC Cytokine Results, Change from Baseline by Visit	Safety
Table 14.3.4.8	Plasma Cytokine Results, Change from Baseline by Visit	Safety
Table 14.3.4.9	INR Laboratory Results, Change from Baseline by Visit	Safety
Table 14.3.5.1	Pulse Rate, Change from Baseline by Visit	Safety
Table 14.3.5.2	Diastolic Blood Pressure, Change from Baseline by Visit	Safety
Table 14.3.5.3	Systolic Blood Pressure, Change from Baseline by Visit	Safety
Table 14.3.5.4	Oral Temperature, Change from Baseline by Visit	Safety
Table 14.3.5.5	Respiration Rate, Change from Baseline by Visit	Safety

